5.4.2. Blood Sample (or Buccal Swab)

A blood sample (or buccal swab) will be collected at the prescreening period to determine whether the subject is a carrier or noncarrier of the APOE 4 gene.

5.4.3. Demographics, Medical History, and Physical and Neurological Exam

Demographic information, a comprehensive medical history and neurological examination with vital signs occur at the screening visit, and vital signs occurs on the last day of each study period. (see table 1) Data are collected from participants using HCP and National Alzheimer's Coordinating Center (NACC) procedures and forms, including demographic information (age, gender, race, ethnicity), medical and surgical history, hospitalization history, medications and supplements, and family history of Alzheimer's disease. We will also ask questions pertaining to diet, sedentary/active lifestyle, sleep history, fluency in languages, marital status, socioeconomic status, education, and work history, and also obtain information on smoking, alcohol use, caffeine use, and drug use.

5.4.4. Neuropsychological Assessments

AD is characterized by progressive EM deficit at the predementia stage. Current AD diagnosis guidelines recognize EM deficit as a core clinical criterion for typical AD diagnosis (67, 68) and recommend objective decline in EM performance as the starting point of AD clinical onset (69). Practically, AVLT and LMT are the two most common EM assessments that are used in various multicenter studies, including the Alzheimer's Disease Neuroimaging Initiative and the Australian Imaging, Biomarker and Lifestyle Study of Ageing. These tests also can detect accelerated EM decline in cognitively normal APOE 4 carriers (61). Therefore, this study will employ AVLT as objective measurements to evaluate the EM decline and the changes to LEV perturbation. For comprehensive cognitive measurements of CN subjects, all enrolled subjects will be administered the WAIS-IV Digit Span and Coding, RAVLT, Boston Naming Test, and Verbal Fluency: FAS & Animal Fluency.

5.4.5. Neuroimaging Assessments

We will conduct imaging on our research-dedicated GE 3T MRI scanner (Signa Premier) equipped with a 48-channel receive-only head coil, which is FDA-approved, or in situations where a back-up scanner is needed, on our research-dedicated GE MR750 3T MRI scanner with 32-channel receiver coil and software version DV26. We will use adapted multiecho image sequence to conduct this project. Below, we briefly describe the imaging acquisition, parameters, and image types. **The first type of measurement is the T1-weighted high-resolution anatomical images. The second type of measurements is task-driven and resting-state fMRI scans.** The 3T fMRI data will be acquired following the adapted General-electric multiecho image sequence, the acquired multiecho images can be effectively denoised with 3.75x3.75x3.75 mm spatial resolution (70). For fMRI scans, one is for EM and the other is for finger tapping. We will utilize a memory task, which is being employed currently for the Alzheimer's Disease Connectome Project in healthy older adults, including participants with memory disorders. The task involves serial presentation of novel (NV) and previously learned (PL) pictures obtained from a published normative set. During the fMRI scan, NV or PL items are presented sequentially for the duration of the scan, and the task is to decide whether the present item is new or previously learned. The task elicits activation in the bilateral ventral and medial temporal lobes, bilateral hippocampal, and fusiform regions. For the Finger tapping task, we will utilize a task developed at MCW. The task follows a block design where participants alternate between finger tapping and rest, in response to on-screen instructions. This task robustly activates the motor network. For the resting-state fMRI scans, two 8-min scans will be acquired with phase up and phase down encoding, respectively. **The third type is the arterial**

spin-labeling (ASL) cerebral blood flow (CBF) perfusion images. The data acquisition scans, plus patient handling time in and out of scanner, will result in an approximately 1-hour scanning session.

Prior to fMRI scans, subjects will undergo MRI safety screening and mock scanner training, as detailed in sections 7.3. and 7.4., respectively.

5.4.6. Blood Draws

All subjects will undergo a blood draw at the last day of each treatment period and on the last day of the washout period. Samples will be labeled with the study name, study visit number, contents of each collection vial, and the date of collection. Tubes may also be labeled with a barcode for sample management.

5.4.7. Randomization, Study Drug Dispensation, Administration, and Compliance

The Investigational Drug Service at Froedtert Hospital will randomize participants to the treatment conditions.

In Period 1, all study participants will receive treatment with either AGB101 (220 mg, orally, QD) or placebo; in Period 2, all subjects will crossover and receive the other treatment. This is a double-blind study, so both the participants and study team will be blind to the treatment received.

All study treatments (drug and placebo) are dispensed in identical nondescript tablets by the Investigational Drug Service at Froedtert Hospital. Tablets are provided for daily morning doses. Study drugs will be dispensed at baseline and on the last day of the 4-week (-/+ 1 week) washout period. Subjects will be asked to self-administer treatment QD, once in the morning.

Treatment compliance will be monitored by participant self-report at the end of each treatment phase, bottle return and pill count, and analysis of AGB101 blood values at each visit during the study protocol.

Data Management

6.1. The Froedtert Hospital Investigational Pharmacy system will be used to enroll patients and obtain the randomly assigned treatment group. Data forms will be printed, completed, and entered into a database. The database will be monitored for completeness, consistency, accuracy, and timeliness. No patient-identifying information will be stored in the database. To ensure that data are secure from external violation, computer systems containing study data will be password protected, and physical access to the computer systems will be limited.

6.2. Determination of Changes in Network Activity and Concurrent Improvement in EM. The cognitive and MRI/rfMRI datasets will be obtained at baseline (before placebo/AGB101 administration) and on the last day of each 2-week treatment period. These two time points will be denoted $t = 1, 2$. The two 25-subject groups, both of which will receive both placebo and AGB101 at different treatment phase, will be denoted $g = 1, 2$. The set of EM scores for subject s , from group g , at time t will be denoted $Cog(s,g,t)$, where $s = 1, \dots, 25$; $g = 1, 2$; and $t = 1, 2$. The HFC calculated between the hippocampus and the bilateral sensorimotor cortex for subject s , from group g , at time t will be denoted $HFC(s,g,t)$.

6.3. Functional-Connectivity Changes Due to Perturbation. We employed age, years of education, gender, and gray matter (GM) volume as time-invariant covariates to obtain residual variables to determine the HFC changes due to perturbation. We will model the HFC as a function of these nuisance regressors, using the following multiple linear regression equation, and retain the residuals as $HFC_{Res}^+(s, g, t)$ for further analysis:

$$HFC(s, g, t) = \beta_0 + \beta_1 Age(s) + \beta_2 Edu(s) + \beta_3 GM(s) + \beta_4 CSF(s) + \beta_5 Gender(s) + Res(s, g, t),$$

where $\widetilde{HFC}^+(s, g, t) \equiv Res(s, g, t)$. This regression will be performed using all of the data (i.e., all subjects, all groups, and all times). The GM measurement will be conducted with GM concentration and hippocampal volume measurement, as described in our publication and others (71-74). We will test the residuals $\widetilde{HFC}^+(s, g, t)$ using three-factor crossed-nested analysis of variance (ANOVA), with fixed factors of group and

time and a random factor of *subject* nested within *group* (i.e., all subjects will be tested at all times, but the placebo and AGB101groups will contain different treatment phases). We will test for both group and time main effects, as well as for the group \times time interaction. If we find significant main effects or interactions, we will perform post hoc procedures to determine which time and group (i.e., placebo vs. AGB101) combinations are significantly different. In addition to the HFC analysis, we will conduct a DMN analysis 75).

6.4. EM Changes Due to AGB101Perturbation. The two EM scores (AVLT and LMT) will be normalized to Z-score by transforming individual raw test scores according to the mean and standard deviation of the scores for all subjects. Then, Z-scores of each test will be averaged to obtain individual composite memory Z-score, as we have previously published (76). Similar to the above model for HFC changes due to AGB101perturbation, we will model the Cog score, using the time-invariant covariates as nuisance regressors:

$$\Delta EM(s, g, t) = \beta_0 + \beta_1 Age(s) + \beta_2 Edu(s) + \beta_3 GM(s) + \beta_4 CSF(s) + \beta_5 Gender(s) + Res(s, g, t)$$

Define $\widehat{\Delta EM}(s, g, t) \equiv Res(s, g, t)$. We will test the residuals $\widehat{\Delta EM}(s, g, t)$ using a three-factor crossed-nested ANOVA, with fixed factors *group* and *time*, and random factor *subject* nested within *group*. We will test for group and time main effects, as well as the group \times time interaction. If we find significant main effects or interactions, we will perform post hoc procedures to determine which time and group combinations are significantly different.

6.5. Prediction of Changes in Correlation Between HFC and EM Before and After AGB101Perturbation. A multiple linear regression is used to model EM as a linear function of HFC and test the difference in slope and intercept between the AGB101and placebo groups. If the subject is in the AGB101group, $I(s, g) = 1$; if the subject is in the placebo group, $I(s, g) = 0$.

$$EM(s, g) = \beta_{0,0} + \beta_{0,1} I(s, g) + \beta_{1,0} HFC(s) + \beta_{1,1} HFC(s)I(s, g) + Res(s)$$

Here, **HFC(s)** represents baseline HFC for subject s (for simplicity, nuisance regressors are not shown).

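### Section 6.5 relates memory to drug and HFC with no subject or period term, so it does not use the crossover pairing; if both scores per subject are entered, the SEs of its two tested terms are too large by 1/sqrt(1 − rho), with rho not given

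*Protocol*

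**What the plan says.** Section 6.5 (same text in protocol and SAP) describes the model thus: "A multiple linear regression is used to model EM as a linear function of HFC and test the difference in slope and intercept" between drug and placebo. The regressors are a treatment indicator I(s, g), HFC(s) and their product. The equation ends in a single Res(s). HFC(s) "represents baseline HFC for subject s (for simplicity, nuisance regressors are not shown"; sections 6.3 and 6.4 list those nuisance regressors as age, education, gray matter, CSF and gender. The indicator is defined in parallel-group terms: "If the subject is in the AGB101group", it equals 1.

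The design is a crossover. Section 5.4.7 says that "in Period 2, all subjects will crossover and receive the other treatment". Section 6.2 describes two sets of 25 subjects, "both of which will receive both placebo and AGB101 at different treatment phase", with cognition and imaging obtained at baseline and "on the last day of each 2-week treatment period".

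Sections 6.3 and 6.4 both recognise the repeated measures; 6.4, for example, has a "random factor *subject* nested within *group". Section 6.5 has no such term.

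**The concern.** Two memory scores from one person are usually positively correlated. A crossover exploits this by comparing each subject with himself or herself. Ordinary regression with one independent residual does not: it leaves between-subject variance in the error used to test the treatment and HFC-by-treatment terms, the two things 6.5 sets out to test.

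The omission cannot be read as shorthand, because the terms left out of the display are the demographic and volume covariates, and the neighbouring sections name a subject factor when they want one.

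What is at stake is the relationship analysis. The central hypothesis (sections 1 and 4.1) is that lower connectivity goes with better memory under the drug. The protocol summary names a regression of the HFC–EM relationship as its statistical methodology and a change in that relationship as its efficacy assessment. Only 6.5 models this relationship by treatment. A null result from it could not be told apart from an effect of the error term.

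**Working it through.** **Inputs from the documents:** 50 subjects; each completer measured once under each treatment (5.4.7, 6.2); baseline HFC constant within subject (6.5); five nuisance covariates (6.3). The documents give no SE, SD, effect size, power, alpha or within-subject correlation for this analysis, so there is no figure of the plan's own to reproduce.

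**Assumptions:** two-sided 5% test; a paired analysis with 80% power as the reference; rho varied. Rho is the correlation of a subject's two EM scores that remains after covariates, and σ² is the variance of one score after covariates.

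**Reading A: two rows per subject, ordinary regression**

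- *Treatment term at mean HFC.* The estimate is the mean within-subject difference. True variance = 2σ²(1 − rho)/n. The regression reports 2σ²/n.
- *HFC-by-treatment term.* The estimate is the slope of the difference on HFC. With S the sum of squares of HFC about its mean, the true variance is 2σ²(1 − rho)/S and the reported variance 2σ²/S.
- For both, reported SE / true SE = 1/sqrt(1 − rho).
- *HFC slope averaged over treatments.* True variance = σ²(1 + rho)/(2S), reported σ²/(2S). The ratio is 1/sqrt(1 + rho), so this SE is too small.
- *Power for the two tested terms* = Φ(1.960 + 0.842 − 1.960/sqrt(1 − rho)).
- *Actual level of the nominal 5% test* = 2[1 − Φ(1.960/sqrt(1 − rho))].

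| rho (assumed) | SE ratio, two tested terms | Actual level | Power (paired = 80%) | SE ratio, averaged HFC slope |
|---|---|---|---|---|
| 0.2 | 1.12 | 2.8% | 73% | 0.91 |
| 0.5 | 1.41 | 0.56% | 51% | 0.82 |
| 0.6 | 1.58 | 0.19% | 38% | 0.79 |
| 0.8 | 2.24 | 0.001% | 6% | 0.75 |

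Example at rho 0.5: 1.960 × 1.414 = 2.772; 2.802 − 2.772 = 0.030; Φ(0.030) = 0.51.

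**Simulation check** (4,000 trials per setting, 50 subjects, five covariates):

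- With covariates unrelated to EM, the ratios for the two tested terms were 1.41 and 1.38 at rho 0.5, and 2.19 and 2.17 at rho 0.8.
- With covariates explaining 30% of the between-subject variance they fell to 1.27–1.28 and 1.89–1.92 (here 0.5 and 0.8 are the correlations before adjustment).
- The two estimates were identical, to rounding, in the ordinary and the paired regression. Only the SEs differ.
- The paired analysis rejected a true null in 4.0% to 5.8% of trials.

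**Reading B: one record per subject, split equally by treatment**

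The variance of the treatment difference is σ²/25 + σ²/25 = 4σ²/n, against 2σ²(1 − rho)/n for the paired analysis. The SE ratio is sqrt(2/(1 − rho)): 1.58 at rho 0.2, 2.00 at 0.5 and 3.16 at 0.8. The reported SE is valid for the data used, but half of the on-treatment scores are unused.

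**The case against.** The strongest objection is that 6.5 never says it uses two rows per subject. EM(s, g) and Res(s) carry no period or treatment index, and the indicator speaks of a subject belonging to one treatment group. Read literally, that is one record per subject, with independent residuals and correct SEs. The ambiguity is real, and the two-row layout is an inference from 5.4.7 and 6.2. It does not rescue 6.5: Reading B gives up the within-subject comparison for which the crossover was chosen. Nor can (s, g) identify a treatment when both groups defined in 6.2 receive both.

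Second, rho is unknown and the covariates may lower it. This stands, and no single inflation factor can be claimed.

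Third, the outcome may be change from baseline, as in 6.4. With equal variances and correlations across the three assessments, two changes sharing a baseline have covariance σ²(1 − rho) and variance 2σ²(1 − rho). Their correlation is 0.5 whatever the raw rho, and the factor under Reading A is 1.41. That is right if 6.5 means change, but its equation is written for EM itself.

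Fourth, the primary HFC analysis (6.3) and the EM change analysis (6.4) both have a subject factor, and sections 6.6 and 7.9 already warn that significance for memory may not be reached. This limits the consequence to the HFC–EM relationship but does not remove it there.

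**Conclusion.** The point holds as a defect of specification in 6.5. As printed, the model has no subject or period term, and under either reading it fails to use the pairing. Under Reading A the tests of the two terms of interest are conservative for any positive rho, by 1/sqrt(1 − rho). Under Reading B the SEs are honest but sqrt(2/(1 − rho)) times those of the paired analysis. The power figures rest on an assumed two-sided 5% level and an assumed 80% reference power.

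A reader might infer three stronger things that the documents do not support:

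- *That the SEs are 1.4 to 2.2 times too large as a matter of fact.* That range needs rho between 0.5 and 0.8 after covariates, and no rho is given.
- *That most of the power is lost.* More than half is lost only if rho exceeds about 0.59 (from 80% power) or 0.66 (from 90%). At rho 0.5 the fall is from 80% to 51%.
- *That all of the model's SEs are inflated.* Only those of the treatment and HFC-by-treatment terms are. In simulation the SEs of the placebo intercept and placebo HFC slope were about right (ratios 0.93 to 0.97), and that of the treatment-averaged HFC slope is too small.

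The change should be made, but the primary analysis does not depend on it.

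**What to change.** State in 6.5 that both on-treatment EM scores are used, index EM and the treatment indicator by subject and period, and replace the single residual by a subject effect plus a within-subject error:

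EM(s, p) = β00 + β01 T(s, p) + β10 HFC(s) + β11 HFC(s) T(s, p) + γ Period(p) + covariates + u(s) + e(s, p),

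with u(s) a random subject intercept and HFC(s) mean-centred, so that β01 is the drug effect at mean HFC and β11 the slope difference. Say whether EM is the score itself or its change from baseline.

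An alternative for completers is to regress each subject's AGB101-minus-placebo EM difference on mean-centred baseline HFC with a centred sequence term. The intercept then tests the drug effect at mean HFC and the slope tests the slope difference. Centring is needed for that interpretation, and the sequence term takes up the period effect. This version drops anyone with only one on-treatment score, which the mixed model keeps.

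The cost is a rewritten equation and some residual degrees of freedom. With 50 completers the difference regression has 50 − 3 = 47, against a nominal 100 − 9 = 91 for two-row ordinary regression with five covariates; the 97.5% t quantile moves from 1.99 to 2.01. The period term may shift the estimates slightly if the sequences are unequal in size or in HFC. No new data are needed.

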Endpoints	
 Primary outcome measurements: Network changes in the bilateral sensory motor cortex regions of the hippocampal functional connectivity after AGB101 perturbation (time frame: 2 weeks) Secondary outcome measurements: Episodic memory performance and neuropsychological test battery as assessed at baseline (Visit 1) and at the post-perturbation procedures (time frame: 2 weeks)
Study Design	
This is a randomized, double-blind, placebo-controlled crossover study in which AGB101 (220 mg, QD) or placebo will be administered to 50 healthy 55–75-year-old subjects (comprising 25 APOE 4 carriers and 25 noncarriers), with the order of treatments counterbalanced in a within-subject crossover design.
 
The study consists of prescreening (Visit –1), baseline/screening (Visit 1), a 2-week treatment period (Visit 2), a 4-week washout period (Visit 3), and a 2-week treatment period (Visit 4).

Study Agent/ Intervention Description	AGB101 Levetiracetam Extended Release 220 mg and placebo will be administered orally, QD
Number of Subjects	50, of which 25 are APOE 4 carriers and 25 are noncarriers
Subject Participation Duration	8 weeks: 2 weeks of AGB101/placebo, followed by a 4-week washout, followed by 2 weeks of AGB101/placebo
Duration of Follow up	None
Estimated Time to Complete Enrollment	18 months
Statistical Methodology	We will employ the multivariate regression model to determine the correlational changes between the hippocampal functional connectivity and the episodic memory due to AGB101 perturbation; we will assume age, years of education, gender, and gray matter volume as time-invariant covariates.
Safety Assessments	Regular data safety monitoring board meetings will be scheduled to monitor progression of the study and review drug adverse events
Efficacy Assessments	Statistically significant changes between the hippocampal functional connectivity and episodic memory relationship at baseline and at the end of the trial
Unique Aspects of this Study	This is the first study to evaluate the safety and efficacy of AGB101 to regulate brain connectivity in cognitively normal subjects at risk for dementia.

Table of Contents

1. Study Objectives	6
2. Background and Significance	7
3. Rationale	9
4. Study Design	9
5. Study Visits and Procedures	11
6. Data Management	13
7. Data Safety Monitoring Plan	14
8. References	22

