1. STUDY OBJECTIVES

Neuropathological, structural, and functional changes related to Alzheimer's disease (AD) may begin insidiously, 20 to 30 years before the manifestation of clinical symptoms. This long, preclinical phase of AD provides a critical window of opportunity to conduct early disease intervention. In this study, we will **test our hypothesis that, during the preclinical AD developmental phase in cognitively normal (CN) older subjects with the apolipoprotein E ε4 (APOE 4) allele, decreased abnormal hyperfunctional connectivity can be correlated with improved episodic memory (EM) using a perturbation, such as AGB101 low dose levetiracetam extended release formulation**. The major pieces of foundational evidence that support our hypothesis are described below.

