1.2. Objective

A low dose of LEV (125 mg, twice daily [BID]) can reduce task-induced hippocampal hyperactivity and improve fMRI task performance in human subjects with MCI. Pioneering studies have demonstrated that, among several antiepileptic drugs, LEV suppresses neural hyperactivity and reverses synaptic and cognitive deficits in AD mice models (19-21). Recent research further demonstrates that a low dose of LEV can reduce task-induced hippocampal hyperactivity in human MCI subjects (22, 23). This proof-of-principle human study suggests that abnormal neural activity may deteriorate memory function (24) and that AD-related neural network dysfunctions are an early and potentially treatable disease component (25-31). So far, no data are available to demonstrate if LEV perturbation can reduce abnormal network activity and concurrently improve memory decline in **CN, older subjects with the APOE 4 allele**. To fill this gap, our specific aim follows:

Specific Aim 1. Determine network-level changes in hippocampal functional connectivity (HFC) after a low-dose AGB101 levetiracetam extended release perturbation (220 mg, QD) for a 2-week period in a randomized, double-blind, and placebo-controlled study with 50 cognitively normal (CN) older subjects (ranging in age from 55 to 75 years), of which 25 are APOE 4 carriers and 25 are noncarriers, and correlate the network changes with the EM before and after a 2-week perturbation with a low dose of AGB101 or placebo.

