4.1. Overall Design

This study will test the hypothesis that **decreased abnormal hyperfunctional connectivity can be correlated with improved EM using a daily, low-dose LEV perturbation (AGB101 levetiracetam extended release)**. In this study, there are two study groups: APOE 4 carriers ($n=25$) and APOE4 noncarriers ($n=25$). The functional connectivity changes in HFC will be determined in a randomized, double-blind, placebo-controlled crossover manner, in which a low dose of AGB101 levetiracetam extended release (220 mg, QD) or placebo is administered to 50 healthy 55-75-year-old subjects (comprising 25 APOE 4 carriers and 25 noncarriers), with the order of treatments counterbalanced in a within-subject crossover design, as illustrated in

Fig. 2 below. The study procedures are almost identical to those described in Refs (77, 78). In brief, study participants will receive placebo during one treatment period and AGB101 levetiracetam extended release during the other treatment period, with the order of treatments counterbalanced (randomized, double-blind).

Figure 2. Study design and AGB101 treatment protocol

Notes: Of the 50 subjects, 25 are APOE 4 carriers and 25 are noncarriers.

See Table 1 for timing and schedule of procedures.

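### Section 6.5, the only model joining HFC and EM, uses baseline HFC, so it tests baseline moderation and only indirectly tests whether HFC and EM change together

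*Protocol*

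**What the plan says.** The aims, in words:

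- Protocol 4.1 (and section 1, in nearly the same terms) gives the hypothesis: "decreased abnormal hyperfunctional connectivity can be correlated with improved EM using a daily, low-dose LEV perturbation".
- Specific Aim 1, in 1.2, says to "correlate the network changes with the EM before and after a 2-week perturbation".
- The Statistical Methodology row of the Protocol Summary describes a regression to "determine the correlational changes between the hippocampal functional connectivity and the episodic memory due to AGB101 perturbation".
- The Efficacy Assessments row looks for "Statistically significant changes between the hippocampal functional connectivity and episodic memory relationship at baseline and at the end of the trial".

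The models:

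- Section 6.3 models HFC alone and 6.4 models EM alone.
- Section 6.5 is headed "Prediction of Changes in Correlation Between HFC and EM Before and After AGB101Perturbation". It regresses EM on HFC in order to "test the difference in slope and intercept between the AGB101and placebo groups". Its terms are an intercept, a 0/1 treatment indicator I(s,g), HFC(s) and their product, with a residual indexed by subject only. HFC(s) "represents baseline HFC for subject s". The SAP repeats this unchanged.
- Section 6.5 says nuisance regressors are left out of the display. Those listed in 6.3 and 6.4 are age, education, gray matter, CSF and gender.

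**The concern.** The hypothesis and Specific Aim 1 are about a change in HFC. The synopsis rows and the 6.5 heading are about a change in the HFC-EM relationship. The one equation that holds both variables contains neither, because on-treatment HFC, which 6.2 indexes as HFC(s,g,t), never enters it. A significant 6.5 interaction could be read as support for the hypothesis when it shows only baseline moderation. A null one could be read as evidence against the hypothesis when HFC and EM do move together. If the intended change-on-change model is not written down now, it will be chosen after the data have been seen.

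Two points of notation add to this. It is unclear what puts a subject in the AGB101 or the placebo group, since 5.4.7 has everyone receive both treatments. And EM(s,g) has no time index, unlike the quantities in 6.2 and 6.4, so it could be an on-treatment level or a change.

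**Working it through.** The documents give no variance, effect size, alpha or power for 6.5, so there is no figure to reproduce. Step 1 needs no numerical assumption. The later steps use assumed inputs and show direction and rough size only.

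**1. What the interaction estimates.** Taking EM as on-treatment EM or its change, 6.5 implies

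E[EM | AGB101] - E[EM | placebo] = β0,1 + β1,1 × baseline HFC.

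So β1,1 is the amount by which the treatment difference in EM varies with baseline HFC. No HFC change appears. Whichever way EM is defined, β1,1 is a baseline-HFC interaction.

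**2. How it connects to the hypothesis.** Let d denote AGB101 minus placebo, c the true slope of dEM on dHFC, and k the strength of the correlation between baseline HFC and its fall on drug. Then

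β1,1 = c × (-k × SD(dHFC) / SD(baseline HFC)).

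Assume EM and baseline HFC in SD units, SD(dHFC) = 0.5, mean dHFC = -0.5 and c = -0.8. This implies a mean EM gain of 0.8 × 0.5 = 0.4 SD, which is generous for two weeks. Then β1,1 = 0.4k, which is 0, 0.12 and 0.24 at k = 0, 0.3 and 0.6.

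**3. Chance of rejection, 50 subjects, paired standard errors.** With ρ the EM correlation between periods,

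Var(dEM | baseline) = 2(1-ρ) + c² × SD(dHFC)² × (1-k²).

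At k = 0.6:
- ρ = 0.5: 1.00 + 0.10 = 1.10; SE ≈ √(1.10/50) = 0.148; estimate/SE = 0.24/0.148 = 1.62.
- ρ = 0.8: 0.40 + 0.10 = 0.50; SE ≈ 0.100; estimate/SE ≈ 2.4.

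Simulated rejection rates (4000 trials per setting) for the baseline-HFC interaction:

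| k | ρ = 0.5 | ρ = 0.7 | ρ = 0.8 |
|---|---|---|---|
| 0 | 5.2% | 4.9% | 5.2% |
| 0.3 | 12.2% | 15.4% | 19.5% |
| 0.6 | 33.1% | 48.4% | 62.1% |

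**4. The converse.** Set c = 0 and let baseline HFC modify the drug effect by 0.4 SD per SD. With both periods pooled by ordinary least squares, the interaction SE is about √(2/50) = 0.20, so the ratio is 0.4/0.20 = 2.0. The test rejects about half the time although HFC change and EM change are not coupled.

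**5. No subject term.** If both periods are pooled by ordinary least squares, the standard errors of the treatment and interaction terms are too large by √((1-R²)/(1-ρ)), where R² is the share of EM variance that the covariates explain.
- R² = 0: √(1/0.5) = 1.41, √(1/0.3) = 1.83, √(1/0.2) = 2.24 at ρ = 0.5, 0.7, 0.8.
- R² = 0.4: 1.10, 1.41, 1.73.

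With no covariates and a true null, a simulation of 50 subjects stacked in this way rejected in under 1% of trials instead of 5%.

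**The case against.** **Baseline prediction may be what was meant.** The preliminary results in 3.3 relate baseline HFC to later EM decline, and 6.6 proposes splitting carriers by HFC activity. Moderation by baseline HFC is therefore a sensible analysis. This stands as a reason to keep the model. It does not make it an answer to the hypothesis or Specific Aim 1.

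**The treatment coding may be shorthand.** A reader might infer that 6.5 analyses a crossover as two parallel arms. The documents do not settle that. Section 6.2 defines g as two 25-subject groups that both receive both treatments, while 6.3 glosses group as placebo versus AGB101. On the 6.3 gloss each subject gives one row per treatment. The notation is ambiguous, and the ambiguity starts before 6.5. What stands is that neither reading shows a subject or period term.

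**A slope-difference equation suits a change in relationship.** This also stands. For the target in the efficacy row and the 6.5 heading, the form of the equation is natural and the HFC input is what does not match. That row need not be rewritten to fit a different model.

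**A change-on-change model may look no better.** At k = 0.6 the model proposed below has 32-63% power, much like the 33-62% in the table. But the first figure rests on 25 carriers and the second on all 50 subjects. Restricted to carriers, the moderation test rejects in about 19-38%.

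**Conclusion.** The mismatch is real and can be read from the page. The words concern HFC and EM changing together, or their relationship changing, and the only joint equation tests moderation by baseline HFC. It responds to the hypothesis only so far as the fall in HFC follows baseline HFC: about 5% rejection at k = 0, 12-20% at k = 0.3 and 33-62% at k = 0.6. Those percentages rest wholly on assumed inputs; the direction follows from the algebra.

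Three stronger readings are not supported.

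- A reader might infer that the plan has nothing bearing on its hypothesis. That goes too far: 6.5 is an indirect test.
- A reader might infer that ignoring the pairing produces false positives. With EM positively correlated between periods beyond what the covariates explain, the treatment and interaction tests err towards missing effects.
- A reader might infer that the main result is at risk. Section 1.3 makes the HFC-EM link neither the primary nor the secondary outcome, and the HFC analysis in 6.3 is not touched by this point. Sections 6.6 and 7.9 already warn that effects on EM may not be detectable in two weeks.

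This should be fixed before unblinding, but it does not undermine the trial.

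**What to change.** 1. Add to 6.5, as the test of the stated hypothesis:

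   dEM = b0 + b1 dHFC + b2 NC + b3 dHFC × NC + b4 HFCbase + b5 HFCbase × NC + b6 Sequence + e,

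   where d is the end-of-period value on AGB101 minus that on placebo, and NC = 1 for APOE 4 noncarriers. Sequence absorbs the period effect in a within-subject difference. Report b1, the carrier slope, with its 95% CI. State that it is correlational and imprecise with 25 carriers, that error in dHFC shrinks it, and that a non-significant result does not refute the hypothesis.

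2. If the sponsor also wants the change in relationship named in the efficacy row, put HFC measured at the same time as EM, HFC(s,g,t), into the existing slope-difference equation, with a random subject effect and a period term. Do not simply reword that row to match model 1.

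3. Keep the baseline-HFC model as a separately labelled moderation analysis, fitted to dEM or with a random subject effect. Define I by the treatment taken in each period, and say whether EM is a level or a change.

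**Cost.** A little more analysis. HFC and AVLT are already scheduled at Visits 1, 2 and 4. The baseline terms in model 1 are needed: with c = 0, moderation of 0.4 and k = 0.6, omitting them gives 19-36% false rejections of the carrier slope, against 4-5% with them when baseline HFC is measured without error. They cost power as k rises: illustratively 46-80% at k = 0 and 32-63% at k = 0.6, for a slope of -0.8. With reliability of 0.7 for dHFC, these become 31-63% and 20-41%.

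Separately, 6.4 builds EM from AVLT and LMT, while the battery in 5.4.4 does not list LMT. That needs reconciling in its own right.
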